# 4.7 Flow Diagram (Clusters)

#### Flow diagram cont/d

#### **5 SCIENTIFIC ABSTRACT**

Around 20% of infants cry for prolonged periods during the first four postnatal months. Where parents cannot cope, this can lead to parental depression, poor parent-child relationships, problems with child development, and infant abuse in rare cases. With National Institute for Health Research Health Technology Assessment (NIHR HTA) support, we have completed a feasibility study to develop the 'Surviving Crying' (SC) package with the aim of supporting parents in this position. 52 parents of excessively crying infants and 50 NHS health visitors (HVs) provided evaluation data. 30 parents met clinical criteria for depression at baseline, halving to 15 after receiving the SC package. Parents' NHS contacts reduced. All 52 parents and 85% of the HVs wanted the package to be included in the NHS. Most (86%) parents were willing to participate in a controlled trial of the package.

**Population:** Parents/carers over 18 years of all backgrounds with a healthy infant up to 20 weeks old who report concern about their infant's excessive crying to their HV.

**Intervention:** Access to the SC support package, SC Booklet, Website, and option of CBT session 1- 6 session delivered to parents by SC Trained HVs, in addition to usual NHS HV services. Comparator: Usual NHS HV services.

**Primary outcome:** Edinburgh Postnatal Depression Scale (EPDS) score measured 8 weeks after baseline.

**Secondary outcomes:** EPDS score at 16 weeks post baseline; proportion of parents with EPDS score of 10 or more, validated measures of parental anxiety, sleep, social supports, parent knowledge of infant crying, amount of infant crying, parents' ratings of how frustrating and problematic the crying is for them, at both 8 & 16-week follow-ups.

**Other measures:** Parental and infant health, breast-feeding persistence; NHS contacts; parents' use and parent and HV ratings of services; at 8 weeks post baseline, health economic measures at both 8 and 16 weeks follow ups.

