#### 7.2.2 Secondary outcome measures

- Edinburgh Postnatal Depression Scale (EPDS) score 16 weeks post baseline; proportion of parents/carers with EPDS score of 10 or more
- Generalised Anxiety Disorder Assessment GAD-7 Scale self-rated measure of anxiety measured at 8 and 16 weeks post baseline.
- EuroQol-5D-5L, self-rated health utility and quality of life measured at 8 and 16 weeks post baseline.
- Parental Confidence Scale (MCQ) measures the confidence of a parent/carer in their parenting role at 8 and 16 weeks post baseline.
- Crying Knowledge Scale measures knowledge of infant crying, amount of perceived infant crying, and parents/carers' ratings of how frustrating and problematic the crying is for them, at 8 week post baseline follow-ups.
- Partner Relationship Quality (CSI-4) measures the relationship satisfaction at 8 and 16 weeks post baseline.
- Health, breast–feeding maintenance will measure parental and infant health, breast-feeding persistence at 8 weeks and 16 weeks post baseline.
- Health economic measures will be assessed at 8 weeks and 16 weeks post baseline.
- Contacts with the NHS; parents' use and parents' and HVs' ratings of services to be collected and measured.

Outcome measures	Deceline Measures	0.14/1		
Outcome measures	Baseline Measures.	8 Week	16 Week	
	(Consent to study)	(From Baseline Assessment)	(From Baseline Assessment)	
		Follow up Measures	Follow Up Measure	
Visit Window	(Within 3 working days of identification of parent/carer)	(+/- 1 week within follow up due date)	(+/- 1 week within follow up due date)	
EPDS	$\checkmark$	$\checkmark$	~	
GAD7	$\checkmark$	~	~	
EQ-5D-5L	~	✓	✓	
Parenting Confidence	✓	✓	✓	
Questionnaire				

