# 8.2 Participant Inclusion criteria

• Parents/Carers aged 18 years or older with an infant up to 20 weeks old (at time of consent), who express concern about their infant's excessive crying.

• Written informed consent

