#### 9.5 Follow up

Follow-up assessments will take place at 8 and 16 weeks after baseline assessment, (which should be completed -1/+1week of the due date). The researcher will telephone or text the participant with appointment times. The researcher will go through each of the questionnaires with the participant in order to complete them. This can be undertaken via the telephone/video call or at the participant's home. Parental/Carer Evaluation of how they found the care they received has the potential to unblind the researcher, therefore the researcher will give a questionnaire to the participant to capture their views of the package received, both groups will also be asked about sharing of the SC materials. This will be completed by the participant not in sight of the researcher (blinded to allocation) and returned in a sealed signed envelope to the research administrator (unblinded to allocation). If the follow up appointment is completed over the telephone /video call, this will be emailed to the participant from the research administrator (unblinded) and requested it is emailed directly back to a secure access restricted email address. Data relating to this will be entered by the research administrator into the SC database, managed by the Leicester Clinical Trials Unit.

To support parents/carers and HV involvement and minimise differential recruitment or follow-up, parents/carers in both groups will be advised at the point of consent by the research team, that their GP will be notified of their participation by letter. However, only when the participants has completed their 16 week follow-up assessment and their participation in the trial has concluded, will the GP be informed of which group the participant was allocated to, intervention or control group. Any parents/carers still concerned about their infant's excessive crying at follow-up or those who require further support will be advised to contact their Regular HV or contact their GP. The GP will also be informed of this.

Participants in the **control group** can request a copy of the SC booklet or access to the SC website intervention resources if required on completion of their involvement in the trial.

To recognize their contribution to the research, participants in both the intervention and control groups will be given a £30.00 shopping voucher at their 16 week follow-up and where indicated on the consent form a summary of the trial findings upon completion and publication of the trial.

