# 14.3 Statistical analysis plan

Statistical analyses will be undertaken according to a pre-trial Statistical Analysis Plan (SAP) written prior to database lock. Descriptive characteristics at baseline will be presented by treatment arm.

The LCTU Trial Statistician will be responsible for planning, monitoring and carrying out data analyses throughout the study, supervised by the LCTU Principal Statistician. The trial will be analysed and reported following the CONSORT statement for cluster RCTs.

The primary analysis will be performed using generalised estimating equations (GEE), which require a minimum of 40 clusters in order to produce reliable estimates. An Analysis of Covariance (ANCOVA) approach will be used with each participant's continuous EPDS score at 8 weeks follow-up as the outcome variable, adjusting for their EPDS at baseline and for the baseline cluster mean, with GEE to allow for differences between clusters. The model will also include a categorical variable for randomisation group and terms for the stratification

factors. The GEE model specification will include a log link function and a Gamma family distribution assumed for the outcome.

The primary analysis will analyse complete cases (i.e. missing data will not be replaced) and participants will be included in the group to which they were randomised irrespective of the intervention received. Secondary analyses will repeat the analysis on both an intention-to treat and per-protocol basis. Missing data will be imputed using multilevel multiple imputation methods in order to account for the clustered nature of the data.  Exploratory analyses of the primary outcome will investigate the effect of differing levels of compliance over and above the minimum level. Secondary outcomes will be analysed using a complete case population, in a similar manner to the primary outcome, modelled assuming an appropriate distribution family and link function. A sensitivity analysis of the primary outcome will adjust for ethnicity and social deprivation index at the individual level. Subgroup analyses of the primary outcome will be performed on the following factors: clusters participating in ICON, SC HV practitioner trained in CBT, social deprivation index and ethnicity.

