Measuring other NHS, PSS and broader societal costs: The costs we include have been informed by our feasibility study and the economic evaluation accompanying the PoNDER trial. We will collect data on use of NHS services occurred during the 12 months before the birth of the child and after their birth due to excessive crying. The data on resource consumption due to excessive crying will be collected during the follow-up period using retrospective questionnaires that parent/carers will be asked to fill in at baseline (covering the period from birth), 8 weeks (covering the period since baseline) and 16 weeks

(covering the period since 8 weeks). This will include contacts and remedies for excessive crying for either the infant or parents/carers. In the feasibility study, resource use data were collected for 52 participants (91%) at all follow-up points and there were non-zero contacts due to excessive crying for the following types of contact:

- a) Health visitor (HV) home visit
- b) HV clinic visit
- c) HV contact by telephone
- d) GP surgery visit
- e) GP contact by telephone
- f) Nurse home visit
- g) Midwife home visit
- h) A&E department
- i) Outpatient visit
- j) Walk-in-centre visit
- k) Health centre visit

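### Resource-use recall periods: a parent who misses week 8 is never asked about weeks 0–8, and the since-birth baseline count mixes rate of use with infant age (minor)

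*Protocol*

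**What the plan says.** Section 14.4 fixes three recall periods for the resource-use questionnaires: "baseline (covering the period from birth), 8 weeks (covering the period since baseline) and 16 weeks", the last "covering the period since 8 weeks". It also mentions NHS use in the 12 months before birth, which does not alter the point.

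Section 8.2 admits "Parents/Carers aged 18 years or older with an infant up to 20 weeks old (at time of consent") and states no lower age. Baseline assessment follows consent immediately (section 9.2), so the baseline recall period is in effect the infant's age. Section 9.5 sets the visit timing: "Follow-up assessments will take place at 8 and 16 weeks after baseline assessment, (which should be completed -1/+1week of the due date").

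Section 7.2.2 lists "Contacts with the NHS" as a secondary outcome without a time point or unit. The abstract (section 5) places it among other measures: "NHS contacts; parents' use and parent and HV ratings of services; at 8 weeks post baseline". Section 14.3 says "Secondary outcomes will be analysed using a complete case population, in a similar manner to the primary outcome", with family and link left open. The primary model adjusts for the participant's baseline EPDS and the baseline cluster mean. The cost analysis in section 14.4 is a difference in mean cost between groups, with no baseline-cost covariate stated and with multiple imputation for missing resource use.

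**The concern.** The recall periods are a matter of data collection. What a form does not ask cannot be recovered by analysis, only imputed. The 16-week form starts at week 8 whether or not the week-8 form was completed. A missed middle visit therefore removes the first half of follow-up from the contacts and cost data, even for a parent who stays in the trial.

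The second issue is comparability. Follow-up forms each cover about 8 weeks, while the baseline form covers whatever time has passed since birth. Two parents with the same weekly use but infants of different ages report very different baseline counts. If that count becomes the baseline covariate, individually and as a cluster mean, part of what it carries is infant age. A simple before/after comparison of contacts would also shift by construction. That is a realistic temptation, because sections 5 and 6 cite reduced NHS contacts in the uncontrolled feasibility study as support for the package.

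**Working it through.** The protocol gives no figure for the analysis of NHS contacts, so there is none to reproduce.

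**1. Length of each recall period**

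| Form | Period | Length |
|---|---|---|
| Baseline | birth to baseline | up to about 20 weeks; no minimum stated |
| 8 weeks | baseline to first visit | 8 ± 1 = 7 to 9 weeks |
| 16 weeks | first to second visit | 15 − 9 = 6 to 17 − 7 = 10 weeks |

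**2. A missed 8-week visit**

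- Both visits attended: weeks 0–8 and 8–16 are asked about.
- Week 8 missed, week 16 attended: only weeks 8–16 are asked about, so 8/16 = half of follow-up is lost.
- Under section 9.4 the first CBT session should come within 3 working days of the request reaching the trained health visitor, and sessions must end within 6 weeks of the first. For a parent who asks at the outset, CBT falls inside the lost period.
- Number affected: the 12% allowance in section 14.1 gives 392 × 0.12 ≈ 47; the 9% loss in the feasibility study gives 392 × 0.09 ≈ 35. Both are ceilings, since some of these parents would miss week 16 too.
- If the 16-week form ran from the last completed assessment, these parents would recall 16 ± 1 = 15 to 17 weeks. The baseline form already accepts up to about 20.

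**3. What the baseline count measures**

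With weekly rate λ and infant age a, a steady rate gives an expected baseline count of λa and an expected 8-week count of 8λ. At equal λ, ages of 20 and 2 weeks give baseline counts in the ratio 20/2 = 10. With no change in behaviour, expected contacts would rise by a factor of 8/2 = 4 for the younger infant and fall to 8/20 = 40% of baseline for the older one. (The 2-week age is illustrative.)

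The size of the effect depends on inputs that the documents do not give, so all of the following are assumptions.

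- *Steady rate from birth; ages uniform from 0.5, 2 or 6 up to 20 weeks; mean 0.1, 0.3 or 0.6 contacts a week; between-parent CV 0.5 or 1.0.* The raw count correlates 0.22–0.62 with age and 0.39–0.87 with the parent's own rate. Residual variance of follow-up contacts is 1.00 to 1.58 times that obtained with an age-corrected, shrunken rate.
- *Steady rate; ages 2–20 weeks; mean 0.5; Gamma shape 1.* R² for 8-week contacts is 0.491 with the raw count and 0.636 with count/age. Residual variance ratio: (1 − 0.636)/(1 − 0.491) = 0.715 in favour of dividing.
- *Same, but crying-related contacts accrue only over the last 1–6 weeks before entry.* R² is 0.41 with the raw count and 0.29 with count/age. Ratio: (1 − 0.29)/(1 − 0.41) ≈ 1.20, so dividing is now worse.
- *Steady rate, minimum age 0.5 weeks, mean 0.1, CV 1.0.* R² is 0.172 raw and 0.153 divided; a very small divisor adds noise.

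Entering age as a covariate next to the count was never worse than the count alone in the scenarios tried. In a linear model this is nearly automatic, at the price of one parameter.

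**4. Effect on the randomised comparison**

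1,500 simulated trials per setting, 86 × 4 = 344 analysed, clustering ignored, steady 0.3 contacts a week, CV 0.7, ages 1–20 weeks, Poisson model with robust standard errors. True rate ratio 0.8, so log ratio −0.223.

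| Baseline covariate | Mean estimate | SD under null | Power |
|---|---|---|---|
| none | −0.219 | 0.105 | 54% |
| raw count | −0.219 | 0.094 | 61% |
| smoothed log rate | −0.218 | 0.089 | 69% |

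Type I error was 5.6–5.9% throughout. The count entered untransformed and the rate on the log scale, so part of the step from 61% to 69% reflects scale rather than age.

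**The case against.** The strongest reply is that most of this belongs to the SAP. Section 14.3 states baseline adjustment for EPDS only. It leaves family and link open for secondary outcomes, and nothing rules out an offset, a rate or an age term. Section 14.4 plans no baseline-adjusted cost model. Missing resource use is already to be imputed, section 11.1 expects little loss, and a longer recall period trades missingness for recall error. All of this stands, and it is why the point is minor. It does not answer the wording of the 16-week form, which no SAP text can repair.

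A reader might go further and infer that the protocol plans to adjust for a raw count driven by infant age rather than by use, and that the treatment comparison is therefore distorted. The documents do not support that. No raw-count covariate is specified. In most assumed scenarios the count follows the parent's rate more closely than age. Infant age is balanced in expectation, and the simulated estimates and error rates were essentially the same whichever covariate was used. Even the raw count did better than no adjustment.

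A reader might also infer that baseline contacts should simply be divided by weeks since birth. Section 14.4 counts contacts due to excessive crying, which need not accrue from birth, and step 3 shows that division can lose precision as well as gain it.

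**Conclusion.** The point holds as a minor one, in two parts.

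- **Form wording.** As written, weeks 0–8 are lost for any parent who misses week 8 and returns at week 16. This follows from the text alone. The number affected is unknown but at most about 47 on the protocol's own allowance, and probably well below that.
- **Baseline count.** If contacts are analysed with a baseline contact covariate, the since-birth count mixes rate of use with observation time. The consequence is some loss of precision on a secondary outcome that the abstract ranks lower still, with no bias in the randomised comparison. The size, and even whether dividing by age would help, depends on contact rates, ages at entry and when crying-related contacts begin, none of which the documents give.

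The primary outcome is untouched, and so is the mean-cost comparison as specified, apart from the data lost at a missed week 8.

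**What to change.** - In section 14.4 and on the questionnaire, let the 16-week form cover the time *since your last completed assessment*, and record the dates covered on every form. Cost: one change of wording, and recall of about 16 weeks for the few affected.
- In the SAP, if a baseline contact count is used as a covariate, include infant age at baseline alongside it and do not divide the count by age. Cost: one covariate, from information available at entry.
- State that raw change in contacts from baseline to follow-up will not be read as an effect, because the periods differ in length. Cost: one sentence.

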Assessing health economic outcomes: QALYs per parent/carer will be calculated based on the health related quality of life (HRQoL). HRQoL will be measured using the EQ-5D-5L which we will collect at each time point. Our feasibility study showed it was feasible to measure HRQoL in parents using the EQ-5D-5L so we use this measure over the SF-6D (which was used in the economic evaluation accompanying the PoNDER trial): it was completed by 100% parents at baseline (57/57) and 89% at follow-up (51/57), with no errors or missing data in the completed returns. Parent-specific utility profiles will be constructed assuming a linear trend between each of the patient's EQ-5D-5L scores at each follow-up point, by measuring the area underneath this profile. Deriving QALYs for infants during the first weeks of life is problematic given their physical and cognitive ability at such a young age, their dependence on parents and other family members, and the lack of appropriate and relevant generic quality of life measures.  Therefore, cost-utility analyses will focus on measurement of utilities among parents only. We will calculate QALYs for the primary caregiver and for both parents where available and present results as mean QALYs per parent/carer in each trial group. Other outcomes to be included in the economic analysis (parental depression, interruption free nights) will be collected directly in the trial.

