Analysis: Multiple imputation by chained equations will be used to deal with missing outcome and resource use values. The multiple imputation equation will include baseline variables showing a significant association with the trial outcomes alongside the pre-specified subgroups: clusters participating in ICON, SC HV practitioner trained in CBT, social deprivation index and ethnicity and their interaction terms. Subsequent analyses of imputed data will use the Rubin's rule to account for additional variability introduced into parameter values as a result of the imputation process.  Cost-effectiveness will be calculated as the mean cost difference between groups divided by the mean difference in outcomes (QALYs, parental depression, interruption-free nights) to give the incremental cost-effectiveness ratio (ICER) and (in the case of QALYs) incremental net monetary benefits (incremental NMBs). We will subject the results to extensive deterministic (one-, two- and multi-way) and probabilistic sensitivity analysis. For the latter, non-parametric methods for calculating the uncertainty around the mean cost and outcome differences will be ascertained using a non-parametric bootstrap.  The bootstrap replications will be used to construct cost-effectiveness acceptability curves, which will show the probability that each strategy is cost-effective for different values of the NHS' and society's cost-effectiveness for an additional unit of outcome.17 Likewise, the bootstrap replications will be used to calculate the 95% confidence interval around the mean NMBs and incremental NMB.

We will combine data on incremental costs with epidemiological data on projected numbers and undertake a budget impact analysis to evaluate what the total cost impact of rolling out the use of the SC package strategy would be were it to be scaled up. We will also use the probabilistic sensitivity analyses combined with the epidemiological information on projected numbers to undertake a value of information analysis to evaluate the potential economic value of future research on this topic.

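### Baseline EQ-5D-5L carries a quarter of each QALY, but section 14.4 names no baseline adjustment of the QALY difference

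*Protocol*

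**What the plan says.** EQ-5D-5L is taken at baseline, 8 and 16 weeks (outcome table, sections 7.2.2 and 7.3). Section 14.4 describes it as a measure "which we will collect at each time point". QALYs are built from it: "Parent-specific utility profiles will be constructed assuming a linear trend between each of the patient's EQ-5D-5L scores at each follow-up point". Each parent's QALY is then obtained "by measuring the area underneath this profile".

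The Analysis paragraph of section 14.4 gives the estimator: "Cost-effectiveness will be calculated as the mean cost difference between groups divided by the mean difference in outcomes". Uncertainty around the mean cost and outcome differences "will be ascertained using a non-parametric bootstrap", and the replications feed the acceptability curves and the net-benefit intervals. Baseline variables are mentioned once in that paragraph, for handling missing data: "The multiple imputation equation will include baseline variables showing a significant association with the trial outcomes alongside the pre-specified subgroups".

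Section 14.3 specifies the clinical analysis of 8-week EPDS as an ANCOVA fitted by GEE, "adjusting for their EPDS at baseline and for the baseline cluster mean", with terms for the stratification factors as well.

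**The concern.** A QALY that starts from baseline utility contains a component that treatment cannot have influenced. Any difference between the arms in that component goes straight into the QALY difference. Because utilities within a parent are correlated over time, the same imbalance also shows up in the 8- and 16-week scores. Over 16 weeks the QALY differences at issue are small: a utility gain of 0.05 at both follow-ups is worth 0.05 × 12/52 = 0.0115 QALY. A modest chance imbalance is therefore not negligible beside the effect being estimated.

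Section 14.4 is otherwise fairly specific. It names chained-equation imputation and its covariates, Rubin's rules, the bootstrap and value-of-information analysis. An analyst working from it would have no instruction to adjust QALYs for baseline utility, although that utility is already collected. The ICER, net monetary benefit, acceptability curves and value-of-information results would all inherit the extra variability.

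**Working it through.** **Inputs from the protocol.** Visits at 0, 8 and 16 weeks; 164 analysable participants per arm; design effect 1.17; ICC 0.037 (section 14.1). The design effect was derived for EPDS and is borrowed here for EQ-5D-5L.

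**Assumed, because the protocol gives no figure.** EQ-5D-5L utility SD s = 0.15 to 0.25, and a common correlation ρ = 0.3, 0.5 or 0.7 between any two visits.

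1. *The plan's own sample size reproduces.* Per arm, (1.960 + 1.282)² × (1/3.78 + 1/3.06) / [ln(10.5/8.5)]² = 139.2, rounded up to 140, so 280 in total. CV = ((12 − 2)/4)/4 = 0.625. Design effect = 1 + ((0.625² + 1) × 4 − 1) × 0.037 = 1.169. Then 280 × 1.17 = 327.6, so 328, or 164 per arm. No figure is stated for the economic comparison itself.

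2. *Weights.* The trapezoid rule gives QALY = (4·u₀ + 8·u₈ + 4·u₁₆)/52. Baseline therefore carries 4/16 = 25%. This follows from the visit schedule alone. A baseline imbalance of 0.05 adds 0.05 × 4/52 = 0.0038 QALY mechanically.

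3. *Total sensitivity to baseline.* With carry-over to the later visits, the slope of QALY on u₀ is (4 + 12ρ)/52.

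4. *Size of chance imbalance.* SE of the baseline difference = s × √(2 × 1.17/164) = 0.1195 s, that is 0.018, 0.024 and 0.030 at s = 0.15, 0.20 and 0.25.

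5. *Precision gain.* R² of QALY on baseline utility = (0.25 + 0.75ρ)² / (0.375 + 0.625ρ). The adjusted SE is the unadjusted SE × √(1 − R²).

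| ρ | slope | R² | SE ratio | SE reduction | one-SE shift, s = 0.15 | s = 0.20 | s = 0.25 |
|---|---|---|---|---|---|---|---|
| 0.3 | 0.146 | 0.401 | 0.774 | 23% | 0.0026 | 0.0035 | 0.0044 |
| 0.5 | 0.192 | 0.568 | 0.657 | 34% | 0.0034 | 0.0046 | 0.0057 |
| 0.7 | 0.238 | 0.739 | 0.511 | 49% | 0.0043 | 0.0057 | 0.0071 |

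The SE reductions do not depend on s. They correspond to effective sample sizes 1.67, 2.32 and 3.83 times as large. At s = 0.20 and ρ = 0.5 the SE of the QALY difference is 0.0061 unadjusted and 0.0040 adjusted.

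6. *Simulation check.* 4,000 trials with no treatment effect, 82 clusters of 4, ICC 0.037, s = 0.20 and ρ = 0.5. The SD of the estimate was 0.0060 unadjusted and 0.0040 adjusted. Its correlation with the baseline imbalance was 0.76 unadjusted and about 0 adjusted. The mean was about 0 for both.

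**The case against.** The strongest reply is that a reader might infer that the plan commits to raw, unadjusted means, and the protocol does not say so. Neither word appears in section 14.4. The quoted sentence defines the ICER, and regression-adjusted mean differences satisfy it equally. Section 14.1 describes the clinical comparison in similar terms, as a difference in mean EPDS, although section 14.3 adjusts it. Section 14.3 also says secondary outcomes, which include EQ-5D-5L, are analysed in a similar manner to the primary. Covariate detail may be in the analysis plan, which is not shown. This stands, so the point is that the adjustment is unstated, not that it has been ruled out. The statement about secondary outcomes does not expressly reach the QALY or ICER step.

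Three other stronger readings also fail:

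- *Bias.* Chance imbalance averages to zero over randomisations. The shift is conditional on the imbalance that occurs, and its unconditional cost is precision.
- *Systematic imbalance.* Later parents join teams already allocated, which might suggest selective recruitment. However, section 9.3 keeps regular health visitors and consenting researchers blind to allocation, and section 9.5 acknowledges accidental knowledge of allocation as a risk and monitors recruitment by team. The figures above rest on chance alone.
- *Extension to EPDS.* The 25% weight applies only to QALYs. The 8-week EPDS score does not contain the baseline score, so under chance imbalance an unadjusted EPDS comparison has no such built-in component and mainly loses precision.

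**Conclusion.** The point holds as a gap in what section 14.4 states. The only estimator written for the economic comparison is a difference in means, baseline variables enter only the imputation model, and a quarter of each QALY is the baseline score. The 25% follows from the schedule. The rest depends on the assumed SD and correlation and on borrowing the EPDS design effect. Over the ranges shown, adjustment would cut the SE of the QALY difference by about 23% to 49%, and a one-SE imbalance would move the unadjusted difference by about 0.003 to 0.007 QALY. For scale, a sustained utility gain of 0.02 is worth 0.02 × 12/52 = 0.0046 QALY and one of 0.05 is worth 0.0115. Adjustment is worthwhile at every assumed correlation. If the analysis plan already specifies it, only the protocol wording needs aligning.

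**What to change.** In the Analysis paragraph of section 14.4, state that incremental QALYs are estimated by regression on arm, baseline EQ-5D-5L utility and site, allowing for clustering by health visitor team. State also that this adjusted difference is the one used in the ICER, net monetary benefit and bootstrap, with the regression refitted in each replicate.

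Two related points should be settled at the same time:

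- *Costs.* If incremental costs are adjusted for baseline resource use, express that use as a rate or also adjust for infant age. The baseline questionnaire covers the period from birth (section 14.4) and infants may be any age up to 20 weeks at consent (section 8.2), so the recall period differs between parents.
- *EPDS-based ICER.* Use a baseline-adjusted mean difference in EPDS points that is consistent with the primary model. That model has a log link, so its coefficient is a ratio of means and cannot serve directly as the denominator.

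The cost is a few sentences and a regression in place of a comparison of means, agreed before database lock. Baseline EQ-5D-5L, site and team are already recorded, so no new data are needed.
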